Title: Stand if You Can: A Standing Intervention in Long Term Care

NCT Number: NCT03796039.

Version Date: May 1 2020

METHODS

Study Setting

The *Stand if You Can* trial is a multi-center, parallel group, RCT using intention-to-treat analysis. For pragmatic reasons, this trial is a single blinded study. It will take place in four different LTC facilities within two cities in the Province of New Brunswick, Canada. Two of the selected facilities will be in each city. Each facility is designated by the Province of New Brunswick as a level three LTC facility (1). This means that the clients have health limitations which require assistance and supervision on a 24-hour basis (1,2). Three of the four facilities are sister nursing homes, meaning they follow the same policies, similar procedures, and have identical floor plans. Registered nurses, licenced practical nurses and rehabilitation assistants are regular staff at all the participating homes. Each of the chosen LTC facilities have the space and resources necessary to assist in the operation and delivery of the trial.

Participant timeline

All of the outcome variables, and participant characteristics will be collected at pre (T1) and post (T2) testing. Data regarding fall information will have two additional data collection time points, including 6 months prior to the intervention (-T) and 6 months follow-up (T3). Attendance will be collected during the intervention, between T1 and T2. See Figure 1 for timeline.

Eligibility Criteria

Inclusion criteria:

- 1) Participants must be a resident of one of the four participating LTC facilities at the time of recruitment.

- 2) Participants must be able to provide consent or have Substitute Decision Maker agree on their behalf to participate in the study if required.
- 3) Participants must be able to walk for 10 meters, with or without a walking aid.

Exclusion Criteria:

- 1) Residents identified by the LTC facility's rehabilitation staff as being too high risk for falling, or unable to participate for safety reasons.

Interventions

Social Standing Intervention

Participants residing in one of the facilities randomized to the intervention will be offered up to 100 minutes of supervised standing per week, for 22 weeks. To achieve 100 minutes of standing each week, participants will stand (either on their own or with a group of their peers) for ten minutes at a time, twice per day, five days per week (Monday-Friday). Participants will be allowed up to five breaks per session of undefined length to assist in attaining the objective of 100 minutes of standing per week. During the standing time research assistants (RA) will engage socially with the participants, with a 1:4 ratio of RA and participants. If the LTC facility is hosting a stationary group activity during the standing time participants will be allowed to partake, provided they can do so while standing. If a participant is able, they will be allowed to stand for 20 consecutive minutes by week 11 and onward, as opposed to two separates 10-minute sessions. The opportunity to have two separate sessions will still be an option for those who do not wish to stand for 20 minutes in one session. A session will be terminated if the maximum time is reached, if the participant takes all five permitted breaks, or if the participant requests to stop or shows signs of physiological distress. Participants will be encouraged to stand five days each week. However, if the participant displays strong verbal disinterest, refuses participation, is

non-compliant, or is physically unable to attend, they will be allowed to miss the planned session. Participants will not be excluded from the study or subsequent analyses due to non-compliance to the intervention. Following a request from a consenting participant, LTC facility staff, or the Substitute Decision Maker will a participant no longer be asked to participate in the standing sessions. Adherence to the intervention will be monitored and tracked using a daily log. Participant attendance, total standing time, number of breaks taken, and total group size (if applicable) will be recorded at each session. These logs will be kept at the local research institution and brought to the LTC facility by RAs each day.

Social Exposure (control)

Participants residing in the control facilities will spend 20 consecutive minutes engaging in social activities with the RA. Social activities will be structured similarly to the intervention group. Some examples include sharing jokes and stories, playing charades, and signing along to music. Social activities will be completed in groups or individually, with participants allowed to join the activity by whatever means of transportation they chose. There will be no limit to the number of participants allowed to attend each group social activity session, with the number of staff ranging from one to two. Adherence to the social activity will be monitored and tracked using a daily log noting attendance, total group size (if applicable), the length of the activity. These logs will be kept at the local research institution and brought to the LTC facility by RAs each day.

Variables and Measures

Participant Characteristics

Participant age, sex, height, weight, medical condition, length of stay in the LTC facility, transfer status, and frailty status will be collected from LTC staff at pre-testing (T1) and post-testing (T2) using the most recent data from participants' LTC health records.

Primary outcome

The primary outcome of this study is gait speed. To measure gait speed, participants will perform a 10-meter walk at pre and post testing, with the first and last two meters used as acceleration and deceleration zones. Gait speed will be measured over the intermediate 6 meters. If required, participants will be permitted to use an assistive device while closely monitored by RA with an available wheelchair made available for safety. Participants will be instructed to walk at a comfortable speed and to start walking when signalled. Using a stopwatch, a RA will manually start timing the participant once the participant's foot or walking aids crosses the 2-meter mark, whichever occurs first. The timer will be stopped once the participant or the walking aid reaches the 8-meter mark and the total time will be recorded in seconds. Once a participant completes the first trial, the participants will take a brief pause and a second trial will be completed. The average of the two values will be used for analysis.

Secondary Outcomes

Physical activity and sedentary behavior will be tracked for seven consecutive days at pre and post testing using an activPAL (PAL Technologies LTD., Scotland, UK). The activPAL will be placed mid-thigh and held in place using TegadermTM tape. Participant sedentary time, upright time, stepping time, total number of steps and total transitions from sitting to standing will be recorded. ActivPAL data will be considered valid if the participant wears the device over at least four consecutive days(3).

Leg power will be assessed using the 30-Second Chair Stand at pre and post testing, following the Senior Fitness Test protocol (4). Participants will be seated in a standardized, armless chair with their arms crossed across their chest. The participant will stand completely and return to a seated position as many times as possible in 30 seconds. RAs will provide guidance as needed during the test for those with cognitive impairments. If participants are unable to complete the test following protocol, their score will be recorded as 0.

Isometric lower leg strength will be assessed using a handheld dynamometer (Lafayette Hand-Held Dynamometer, Lafayette Instrument, Sagamore, USA) at pre and post. The dynamometer will be positioned mid-tibia, with the padding snug against the participant's leg. To ensure each participant experiences the same resistance throughout the test, RA will use a non-elastic woven strap that will interlace around the handle of the dynamometry and chair leg. With arms crossed across their chest, participants will then be instructed to extend their leg as forcefully as possible into the dynamometer for 10 seconds, with peak strength recorded as maximal kilograms (kg) achieved. Leg strength will be assessed twice on each leg, with an additional trial if the first two differ by more than one kg. RA will provide motivational cues and encouragement during each test.

Balance will be assessed using the BrainBlox software (5)on a Wii Balance Board (Nintendo, Kyoto, Japan) at pre and post testing. The balance board measures ground reaction forces that are then computed into centre of pressure measures. Participants will conduct three trials of 30 seconds with eyes open. Participants will stand in a neutral position, feet hip-width distance apart with their arms at their sides. The balance assessment will be conducted three times, with intermittent breaks as needed. If required, participants will be permitted to use an assistive standing device.

Metabolic profile will be assessed as participant high-density lipoprotein, low-density lipoprotein, total cholesterol, triglyceride, and blood glucose using a CardioChek Professional Analyzer system (PTS Diagnostics, Whitestown, Indiana, USA). Following a finger prick conducted using a single use lancet, approximately 60 μ L of whole blood will be collected. Forty μ L will be used to assess blood lipids via a Lipid Panel (PTS Diagnostics, Whitestown, Indiana, USA), with the remaining 20 μ L used to assess blood glucose via a Glucose Panel (PTS Diagnostics, Whitestown, Indiana, USA).

Cognition will be assessed using the Mini-Mental State Examination (MMSE) questionnaire(6). Participants who score 18 or above will be asked to complete subsequent questionnaires pertaining to their psychosocial health. These questionnaires include the Geriatric Anxiety Inventory(7), Falls Efficacy Scale – International (FES-I) (8), Geriatric Depression Scale Short Form (9), the DeJong Loneliness Scale (10) and the UCLA Loneliness Scale (11).

Falls, injuries due to falls, and hospitalization will be collected from the participants accident report provided by the LTC facility. At 6 months follow-up, data will be collected retrospectively from 6 months prior to the intervention and up until the 6-month follow up. This data includes the number of falls, type and number of injuries as well as the number of hospital visits.

Attendance will be collected throughout the intervention. The daily total standing time, number of breaks, the use of an assistive device as well as the group size will be recorded.

Sample Size

Sample size was estimated based on anticipated changes in gait speed, the primary outcome of this trial. The minimum clinically important difference in gait speed is 0.1 m/sec

(18). With a cluster size of two, and assuming a small-to-moderate clustering effect (intraclass correlation coefficient = 0.075), within-group standard deviation of 0.10 m/s, and alpha = 0.05, recruiting 36 participants per group will provide 80% power to detect a clinically important change in gait speed. To account for an expected loss to follow-up of 20%, we plan to recruit 44 participants per group (total n=88).

Recruitment

The Director of Care for each of the LTC facilities will be contacted to aid in the identification of residents who may benefit most from a low-intensity physical activity intervention. A letter will be sent from the LTC facility on behalf of the research team to each potential resident, or their Substitute Decision Maker to inform them of the study. Once the letters are distributed members of the research team will contact residents or their power of attorney to formally inquire about participation and obtain informed consent for participation.

Allocation

RAs not participating in the trial procedures will use a random number generator to construct a permuted-block randomisation list (block size = 2). All participants will be cluster-randomized to the intervention or control group on a 1:1 basis. Group assignments will be concealed from participants, outcome assessors, and research staff completing the data analyses. RA's conducting pre-testing evaluations will be blinded at pre-testing, but will conduct post testing evaluations unblinded, due the diversity of evaluations requiring training and experience.

Data Management

Each participant will be assigned an ID number. All the data collected will be recorded under this number in their participant file. Each file will have the data manually written, and then transferred from the files into an excel on password protected computers. The data will be entered and revised by two different RAs to reduce potential data entry errors. Only researchers engaged in collection, analysis and dissemination will have access to data, with approval of the primary investigators. Hard copies of the collected data will be stored in filing cabinets, in a locked working space at each university. Data will be kept for a period of seven years, at which point it will be destroyed.

Statistical Analysis

As this is an intention to treat trial, all data will be evaluated based on the randomized group allocation. Generalized linear models – specifically an ANOVA analysis, will be used to compare the dependant variable (gait speed) between intervention groups while accounting for potential confounders (e.g., age, sedentary level). Secondary outcomes such as sedentary behaviour, leg strength, sit to stand ability, balance performance, psychosocial outcomes, and blood lipids and blood glucose will each be analyzed with separate linear models as well, in relation to intervention group. Consistent with an intention-to-treat approach, the models will estimate missing values. When possible, general linear models will also be used to evaluate subgroup analyses, where health conditions will be considered a fixed variable in relation to gait speed performance.

1. Standards Manual: Nursing Home Services. Department of Social Development, Government of New Brunswick; 2019.
2. Banjeer A. An Overview of Long-Term Care in Canada and Selected Provinces and Territories. Place Call Home Long Term Care Can. 2009;29–57.
5. C. X. Yang. Low-Cost Experimental System for Center of Mass and Center of Pressure Measurement (June 2018). IEEE Access. 2018;6:45021–33.
10. De Jong Gierveld J, Van Tilburg T. The De Jong Gierveld short scales for emotional and social loneliness: tested on data from 7 countries in the UN generations and gender surveys. Eur J Ageing. 2010/04/09 ed. 2010 Jun;7(2):121–30.

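### The activPAL rule of four consecutive days can discard records with four to six worn days, and the plan does not say whether the variables are expressed per day

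*Combined protocol and SAP*

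**What the plan says.** All the activPAL text is in the Secondary Outcomes section. The recording window is seven days at each of two time points: "Physical activity and sedentary behavior will be tracked for seven consecutive days at pre and post testing using an activPAL". The variables are listed in one sentence: "Participant sedentary time, upright time, stepping time, total number of steps and total transitions from sitting to standing will be recorded". The validity rule follows: "ActivPAL data will be considered valid if the participant wears the device over at least four consecutive days(3", with a methods paper cited in support. The section does not define a valid day, for example by a minimum number of hours worn. It gives no unit of analysis for the variables.

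Under Statistical Analysis, sedentary behaviour is among the secondary outcomes that "will each be analyzed with separate linear models as well, in relation to intervention group". No adjustment for days worn is named. On missing data the section says: "Consistent with an intention-to-treat approach, the models will estimate missing values". It does not name the method. The same section gives sedentary level as an example of a confounder in the gait speed model, without saying how it is measured.

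**The concern.** Two features of the plan sit awkwardly together.

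First, a seven-day record is screened on its longest run. Two residents with the same number of worn days can be treated differently, and a resident with six days can be rejected while one with four is kept. The rejected data have already been collected, so the cost is precision in an outcome close to the purpose of a standing intervention. If residents whose wear is broken up differ from the others, the retained sample is also less representative.

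Second, valid records can contain anything from four to seven days, and the plan does not say that the variables are put on a per-day scale. The choice is left to the analyst.

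Both matter mainly for a secondary outcome. If the sedentary level named as a possible confounder comes from the activPAL, both also reach the primary gait speed model.

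**Working it through.** The documents give no figure for activPAL validity or wear, so there is nothing of the plan's own to reproduce.

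**Inputs**
- Recording window: 7 days (Secondary Outcomes).
- Rule as written: longest run of worn days is at least 4 (Secondary Outcomes, read literally).
- Alternative rule: at least 4 worn days of 7, in any order.
- Probability q that a given day is worn, independent across days: **assumption**, range 0.80 to 0.95. Let p = 1 − q.

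**Step 1. Count the patterns.** There are 2^7 = 128 worn/not-worn patterns. Those with at least four worn days are:

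| Days worn | Patterns | Valid as written | Rejected |
|---|---|---|---|
| 7 | 1 | 1 | 0 |
| 6 | 7 | 6 | 1 |
| 5 | 21 | 9 | 12 |
| 4 | 35 | 4 | 31 |
| Total | 64 | 20 | 44 |

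The one rejected six-day pattern is a miss on day 4, which leaves runs of 3 and 3. A miss on day 1, 2, 3, 5, 6 or 7 leaves a longest run of 6, 5, 4, 4, 5 or 6, and the record stays valid.

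**Step 2. Weight the patterns by probability.**
- As written: P = q^7 + 6q^6p + 9q^5p^2 + 4q^4p^3.
- Any four days: P = q^7 + 7q^6p + 21q^5p^2 + 35q^4p^3.

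At q = 0.90:
- As written: 0.4783 + 0.3189 + 0.0531 + 0.0026 = 0.853.
- Any four days: 0.4783 + 0.3720 + 0.1240 + 0.0230 = 0.997.

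As a check, the first run of four starts either on day 1, or on day 2, 3 or 4 straight after a missed day. So the written rule also equals q^4(1 + 3p) = 0.6561 × 1.3 = 0.853.

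| Days missed | Valid as written | Valid, any four | Difference (points) |
|---|---|---|---|
| 5% | 93.7% | 99.98% | 6.3 |
| 10% | 85.3% | 99.7% | 14.4 |
| 20% | 65.5% | 96.7% | 31.1 |

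The six-day case alone (q^6p) accounts for 3.7%, 5.3% and 5.2% of records at these three rates.

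**Step 3. The opposite wear pattern.** If the device comes off once and stays off, the number of worn days equals the longest run. The two rules then accept exactly the same records, and the difference is zero.

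**Step 4. Unit of analysis.** At the same daily rate, a four-day sum is 4/7 = 57% of a seven-day sum, which is 43% lower. This would matter only if sums over the wear period were analysed.

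**The case against.** The strongest case on the other side is that the rule is prespecified and carries a citation, that the size of the loss rests on an undocumented wear process, and that the unit is merely unstated. Much of this stands.

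- **Raw sums compared.** A reader might infer that four-day and seven-day totals will be set side by side, so that a resident could show a 43% fall with no change in behaviour. The documents do not say so. The sentence on variables describes what is recorded, not the analysis scale. The word total is attached only to steps and transitions, not to sedentary, upright or stepping time. What is supported is that the unit is not specified, and an analyst would probably fill that gap sensibly.
- **Size of the loss.** The device is taped on, and no section describes re-application, so a single permanent removal is quite possible. The loss is then nil. The 44 rejected patterns of 64 are not a loss rate either, because they give three scattered missed days the same weight as a complete record.
- **Compounding over two visits.** Squaring the 10% figure gives 0.853^2 = 73% valid at both visits. This needs independence between a resident's two visits, and it matters most for a change score, which the plan does not specify for activPAL. The plan also says that missing values will be estimated, so an invalid record need not remove the participant.
- **Selection by cognition.** The trial includes residents with cognitive impairment, and a link between impairment and broken wear is possible. No section shows one.
- **The citation.** Whether the cited source supports consecutive days cannot be checked here, so it cannot be said that the rule brings no benefit.

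The missing-data sentence does not remove the point. Estimating a value that was measured and then discarded is no better than using it.

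**Conclusion.** The point holds as a cheap improvement, not as an error that undermines the trial. Read literally, the rule can reject records with four, five or six worn days while accepting an unbroken four-day record. The loss per visit is between zero (permanent removal) and, under independent missed days, 6, 14 or 31 percentage points at 5%, 10% or 20% missed days. Neither the miss rates nor the independence comes from the documents, so these figures show a range and are not a forecast. The missing per-day unit and the missing definition of a valid day are gaps in specification. They are not evidence that unscaled totals will be compared. No bias between the arms and no selection by cognition has been shown. The consequence is confined to the activPAL outcomes, unless the sedentary level used as a covariate for gait speed is taken from the device.

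**What to change.** Amend the Secondary Outcomes section before any comparison by group is made:

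1. Accept a record with four or more valid days of the seven, not necessarily consecutive.
2. Define a valid day in advance, including the minimum wear. The any-four-days rule cannot be applied consistently without this.
3. Analyse every activPAL variable as the mean per valid day. If sedentary level in the gait speed model comes from the activPAL, say so and use the same scale.
4. Report the result under the four-consecutive-days rule as a sensitivity analysis.

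The cost is a few sentences and one extra analysis, with no new data. The small downside is that the main rule may depart from the cited convention; item 4 lets a reader see whether that matters.

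### Leg strength is a peak-effort test with unscripted encouragement, and the plan says the assessors are unblinded at T2; a fixed script would limit the bias this allows

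*Combined protocol and SAP*

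**What the plan says.** The test is described in the combined protocol and SAP under Secondary Outcomes. The instruction for each trial is that "participants will then be instructed to extend their leg as forcefully as possible into the dynamometer for 10 seconds". The score is the highest force reached, "with peak strength recorded as maximal kilograms (kg) achieved". Two features of the procedure are standardised. One is the resistance: "To ensure each participant experiences the same resistance throughout the test, RA will use a non-elastic woven strap". The other is the number of trials: "Leg strength will be assessed twice on each leg, with an additional trial if the first two differ by more than one kg". The last sentence of the paragraph reads "RA will provide motivational cues and encouragement during each test". The words, number, timing and loudness of the cues are not stated.

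On blinding, the Allocation section makes two statements in succession. The first is "Group assignments will be concealed from participants, outcome assessors, and research staff completing the data analyses". The second is "RA's conducting pre-testing evaluations will be blinded at pre-testing, but will conduct post testing evaluations unblinded", and the reason given is that the assessments need trained and experienced staff. Study Setting calls the trial single-blind without saying who is blinded.

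Under Statistical Analysis, leg strength has its own linear model by intervention group. No record of the cues given is planned, and no sensitivity analysis addresses assessor knowledge.

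**The concern.** Peak voluntary force depends on how hard the resident tries, and the assessor is told to influence that. If the assessor knows the arm at T2, the urging can differ between arms, whether or not anyone intends it, at the visit where the effect is read. The coaching instruction gives knowledge of the arm a route to the resident's performance, in addition to any effect on timing or recording. The gait test differs here: it asks for a comfortable pace and contains no instruction to encourage.

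At stake is the interpretation of a secondary outcome. A gain in leg strength would be a natural explanation for any gain in gait speed, so a strength difference arising partly from coaching could mislead. The primary outcome and the sample size are not affected.

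**Working it through.** **1. Who is blinded at T2.** The two Allocation sentences conflict on outcome assessors. The second is specific to the T2 visit and gives a reason, so it is the more likely description of what will happen. The rest of this check assumes unblinded T2 testing.

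**2. Whether the stated controls reach the urging.** The strap fixes resistance, and the dynamometer reading limits discretion in scoring. The extra-trial rule responds to disagreement between a resident's first two trials. Urging applied equally to both trials raises both and does not trigger it. None of these controls equalises effort.

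**3. Whether T1 adjustment helps.** Write the observed strength as

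- T1: Y1 = S1 + c
- T2: Y2 = S2 + c + b × A

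where S is strength under uniform encouragement, c is an assessor's stable coaching style, A is 1 in the intervention arm and 0 in control, and b is the part of the urging that depends on knowing the arm.

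- Change score: Y2 − Y1 = (S2 − S1) + b × A. The style c cancels and b remains in full.
- Adjustment for Y1 with slope β: b again remains in full, because blinded T1 testing carries no trace of it. A difference in c between arms is reduced to (1 − β) times its size.

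T1 adjustment therefore deals largely with stable style, but not with urging that depends on arm. The plan does not name T1 strength as a covariate.

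**4. Size.** The documents give no SD, expected difference or coaching effect for leg strength, so there is no stated strength figure to reproduce and b cannot be derived. What can be shown is the consequence of an assumed b.

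Inputs: 36 analysed per arm (Sample Size), alpha 0.05 taken as two-sided, no true effect, and b in SD units (assumed). The design effect is borrowed from the gait-speed calculation, which reproduces as follows:

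- Without clustering: 2 × (0.10 × (1.960 + 0.842) / 0.10)² = 15.7 per arm.
- Reading the stated cluster figure of two as two homes per arm gives 18 residents per home: 1 + (18 − 1) × 0.075 = 2.275.
- 15.7 × 2.275 = 35.7, or 36 per arm, as stated.

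Chance of a significant strength difference: P = Φ(d − 1.96) + Φ(−d − 1.96), with d = b / √(2/n) and n = 36 divided by the design effect.

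Worked case, b = 0.2:

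- Independent residents: √(2/36) = 0.2357, d = 0.849, P = 0.1332 + 0.0025 = 0.136.
- Design effect 2.275: n = 15.82, √(2/15.82) = 0.3555, d = 0.563, P = 0.081 + 0.006 = 0.087.

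| Assumed shift b (SD) | Independent residents | Design effect 2.275 allowed for |
|---|---|---|
| 0 | 5.0% | 5.0% |
| 0.1 | 7.1% | 5.9% |
| 0.2 | 13.6% | 8.7% |
| 0.3 | 24.7% | 13.5% |
| 0.5 | 56.4% | 29.0% |

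Both columns use a normal approximation. The second applies the gait-speed ICC to strength, which is an assumption.

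**The case against.** The strongest reply is that the root problem is unblinded T2 assessment, not encouragement. That affects every assessor-run outcome, including the hand-timed walk, and assistants may also guide residents with cognitive impairment in the chair stand. This stands: a script would treat one route by which the bias acts, and tone and manner would remain in unblinded hands. The route can still be narrowed cheaply even if T2 stays unblinded, and the staffing reason given for unblinding does not require unscripted cues.

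A second reply is that the absence of a script is inferred from silence. The instruction applies to each test, in both arms and at both visits, and an operations manual might hold the wording. This also stands; if such a script exists, the sponsor need only cite it.

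Three stronger readings are tempting, and the documents support none of them:

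- A reader might infer that different assistants work in different homes, so that one coaching style falls on one arm. The documents describe no such assignment, and a stable style would be present at T1 too.
- A reader might set an assumed bias in kilograms against the 1 kg rule. That rule triggers a further trial within one resident and says nothing about a difference between group means.
- A reader might infer that encouragement is itself an error. In a test of maximal effort it is not; the gap is that it is not standardised.

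**Conclusion.** The concern holds as a minor point. As written, the plan lets knowledge of the arm influence effort at T2 in a peak-effort test, and neither the stated controls nor T1 adjustment would remove the result. This rests on the specific Allocation sentence about T2 prevailing over the concealment sentence before it, and on there being no script elsewhere.

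The documents show that bias is possible. They do not show that it will occur, how large it would be, or which arm it would favour, so a reader should not conclude that a strength difference in this trial would be an artefact. The percentages above show what follows from an assumed shift and do not estimate one.

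**What to change.** Keep the encouragement, but replace the sentence with a fixed script: the same words, number and timing of cues, and voice level, for every trial at T1 and T2 in all four homes. If a script already exists, cite it.

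Reconcile the two Allocation sentences by stating who is blinded at each visit. If T2 remains unblinded, report the leg-strength results as assessed unblinded, because a script reduces this bias but does not remove it.

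The cost is one paragraph in the test instructions, with no added staff, visits or sample size. The downside is slightly lower peaks, or a few more incomplete tests, in residents who need coaxing; the documents give no basis for assuming that this would fall equally on both arms.

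### The stated 80% power at alpha 0.05 does not hold with two facilities per arm: a valid facility-level test has about 35% power on the plan's own inputs, and the planned ANOVA names no facility term.

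*Combined protocol and SAP*

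**What the plan says.** Study Setting: "It will take place in four different LTC facilities", two in each of two cities. The facility is the unit of randomisation. The description of the standing arm begins "Participants residing in one of the facilities randomized to the intervention", and Allocation states that "All participants will be cluster-randomized to the intervention or control group on a 1:1 basis", using permuted blocks of size 2. Each arm therefore has two facilities.

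Sample Size takes 0.1 m/s as the minimum clinically important difference. It continues "With a cluster size of two, and assuming a small-to-moderate clustering effect" (ICC 0.075), gives a "within-group standard deviation of 0.10 m/s, and alpha = 0.05", and concludes that "recruiting 36 participants per group will provide 80% power to detect a clinically important change in gait speed". On attrition it adds: "To account for an expected loss to follow-up of 20%, we plan to recruit 44 participants per group (total n=88").

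Statistical Analysis names an ANOVA within a linear-model framework, which "will be used to compare the dependant variable (gait speed) between intervention groups while accounting for potential confounders (e.g., age, sedentary level"). It names no facility term, random effect, cluster-robust variance or small-sample degrees of freedom.

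**The concern.** The sample size allows for clustering but then uses a reference distribution that suits many clusters, not four. The analysis section does not carry the clustering through at all. This leads to two different failures, depending on what is done.

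- If the ANOVA is run as described, an ordinary difference between homes can be declared an effect of standing far more often than 5% of the time.
- If facility is handled properly, the trial has much less power than stated for its own target, and a non-significant result would say little.

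In neither case does the stated pair (alpha 0.05, 80% power) describe the trial.

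**Working it through.** **Inputs.** From Sample Size: difference 0.10 m/s, SD 0.10 m/s, ICC 0.075, alpha 0.05, 36 analysed and 44 recruited per group. From Study Setting, Social Standing Intervention and Allocation: two facilities per arm. Sidedness is not stated. Two-sided is inferred because 36 per group gives 80% only on that reading (one-sided normal power would be 88%).

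**1. Reproduce the plan's figure.**

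- Without clustering: n = 2 × (1.96 + 0.8416)² × (0.10/0.10)² = 15.7 per group.
- Literal cluster size of two: design effect 1 + (2 − 1) × 0.075 = 1.075, and 15.7 × 1.075 = 16.9, or 17 per group. This is not the plan's figure.
- Two clusters per arm, 18 residents each: design effect 1 + 17 × 0.075 = 2.275, and 15.7 × 2.275 = 35.7, or 36 per group.
- SE = √(2 × 0.10² × 2.275 / 36) = 0.03555. The noncentrality is 0.10 / 0.03555 = 2.813.
- Normal-theory power = Φ(2.813 − 1.960) = 80.3%. At 35 per group it is 79.9%, so 36 is the smallest number that reaches 80%.

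The wording about cluster size is therefore a mislabel for two clusters per arm. Reading 0.10 m/s as the within-facility SD gives 77.2%, so the total-SD reading is the one that fits.

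**2. Use the degrees of freedom that the design provides.** Four facility means less two arm means leaves 2 df. The critical value is 4.303 instead of 1.96. With the same noncentrality, noncentral t gives 35.4%. In simulation (200,000 trials), the t-test on four facility means rejected 5.0% at no difference, 35.5% at 0.10 m/s and 79.7% at 0.20 m/s.

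**3. Vary the assumptions** (2 df, two-sided and 36 per group unless stated).

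| Case | Power for 0.10 m/s |
|---|---|
| Stated inputs | 35.4% |
| 44 per group, no loss | 37.4% |
| Unlimited residents in the same four facilities | 50.4% |
| 0.10 m/s as within-facility SD | 33.5% |
| One-sided 0.05 | 57.6% |
| Block term fitted (1 df), no variance reduction | 17.5% |
| ICC 0.03 | 46.9% |
| ICC 0.01 | 55.1% |
| ICC 0 | 60.5% |
| Assumed baseline correlation 0.5 / 0.7 / 0.8, ICC 0.075 | 43% / 55% / 67% |

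The last row multiplies the SD by √(1 − r²). It applies only if 0.10 m/s is not already an SD of change. The documents give no correlation.

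**4. The ANOVA without facility.** Simulated at ICC 0.075 with 18 residents per facility, it rejects a true null 19.8% of the time. With 22 per facility (44 per group) the figure is 22.9%. At ICC 0.01 it is still 7.0%. Its rejection rate at 0.10 m/s is about 94%, but with a type I error near 20% that is not power at alpha 0.05.

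**5. Attrition (minor).** 36 / 0.80 = 45, not 44; 1 − 36/44 = 18.2%. At 20% loss from 44, 35.2 per group remain and normal-theory power is 79.95%, so the effect is negligible.

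**The case against.** The plan's arithmetic is correct for a standard design-effect formula. The dispute is over the reference distribution and a silent analysis section, not a slip in calculation. That is fair, but the formula still does not fit four clusters.

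The 35% is conditional. Gait speed is measured before and after, and three of the four homes share policies and floor plans, so the ICC could be smaller and baseline adjustment could help. Taken together, these can matter: on 2 df, an assumed baseline correlation of 0.8 gives 81% at ICC 0.03 and 88% at ICC 0.01, while 0.7 gives 70% and 78%. This stands as a caution against quoting 35% without its assumptions. It does not support the stated 80%. At the plan's own ICC, a correlation of 0.8 reaches only 67%. The documents give no correlation and do not name baseline gait speed as a covariate. The section also bases its calculation on anticipated changes, so 0.10 m/s may already be an SD of change.

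The covariate list is open-ended, so a facility term is not excluded. But facility is nested in arm: adding it as an ordinary fixed covariate would confound it with treatment, so the open list cannot supply a valid adjustment.

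The 2-df t-test assumes roughly normal facility means with equal variance, which four facilities cannot verify. Allocation does not say what the blocks of two are; if they are cities and are fitted, only 1 df remains. Both points stand as limits on the design, and neither brings power closer to 80%.

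**Conclusion.** The concern holds, and the Sample Size and Statistical Analysis sections need correction. On the plan's own ICC, SD and difference, a valid two-sided 5% test has about 35% power for 0.10 m/s, not 80%, and about 80% power only for 0.20 m/s. Recruiting more residents in the same four homes cannot take it above about 50% at ICC 0.075. The ANOVA without a facility term would have a type I error of about 20%.

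The 35% rests on a two-sided test, 0.10 m/s as total SD, equal cluster sizes, normal facility means with equal variance, no block term and no gain from baseline adjustment. Changing one of these assumptions at a time, within the ranges above, does not restore 80%. The mislabelled cluster size and the attrition rounding are secondary.

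**What to change.** **Sample Size.** Replace the cluster-size phrase with:

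> With two clusters (facilities) per arm and about 18 analysed residents each (design effect 2.275)

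Replace the power claim with:

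> about 35% power for 0.10 m/s (about 80% for 0.20 m/s), two-sided alpha 0.05, 2 df, assuming total SD 0.10 m/s, equal cluster sizes, no block term and no gain from baseline adjustment

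State whether 0.10 m/s is an SD of change, and that 44 per group covers 18% loss.

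**Statistical Analysis.** Make the primary gait-speed comparison a facility-level inference on 2 df, for example a t-test on the four facility means after resident-level covariate adjustment. Do not enter facility as an ordinary fixed covariate. Naming baseline gait speed among the resident-level covariates is worth considering, since it is already measured at T1. State what the randomisation blocks are and that no block term is fitted, or else restate the degrees of freedom. Report the effect with its 95% confidence interval, and state that a non-significant result will not be read as no effect.

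**Cost.** No new data or recruitment. The stated power is less favourable and the interval wider. The expected half-width on 2 df is about 4.303 × 0.03555 × 0.886 = 0.14 m/s (0.886 is the mean ratio of estimated to true standard error on 2 df), against 1.96 × 0.03555 = 0.07 m/s with the normal value. Only more facilities would lift the 2-df limit. For example, spreading 36 per arm over four facilities per arm (6 df) gives about 79.7%, but that is a different trial and is not needed for this correction.
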